- v* Investigator will examine each participant's joints per the Haemophilia Joint Health Score (HJHS). At baseline, the Investigator will assess the presence of any target joints according to the International Society on Thrombosis and Haemostasis (ISTH) criteria.
- w* For bleeding episodes initially treated at the study sites, the Investigator will contact the caregiver approximately 72 hours from the time the BIVV001 injection was administered to treat the bleeding episode at the study site and record the caregiver's assessment of response to BIVV001 treatment on the eCRF using a 4-point bleeding response scale. For bleeding episodes that are treated at home, caregivers will record response to bleeding episodes in the ePD.
- x* Samples will be collected prior to any BIVV001 dosing and will be archived by the central laboratory (if required) for future research, eg, immunology assays, further coagulation assays, or clarification of any clinical or laboratory AE, etc. This is optional and participants/caregivers will sign an additional consent for this research.
- y* At the screening visit, caregivers will be shown and trained on the ePD device to ensure understanding of obligation to enter data during the trial. Devices will be given to caregivers at the baseline visit.
- z* Caregivers will record all bleeding episodes in the ePD beginning at Baseline. Assessment of response to bleeding episodes will be performed using a 4-point bleeding response scale. The caregiver should record response approximately 72 hours from the time the first BIVV001 injection was administered to treat the bleeding episode, unless treatment of the bleed was administered in the clinic. In that case, the investigator will report the caregiver's response to treatment via the eCRF.
- aa* The first 12 participants in each age cohort will undergo PK sampling after the first dose of BIVV001 (Baseline). Thereafter, PK sampling at Baseline will be optional. See PK sampling details in [Table 2](#).
- bb* Trough and peak samples are collected within 30 minutes prior to rFVIIIFc-VWF-XTEN dosing and 15 (\pm 3) minutes post-injection, respectively. This trough sample should be collected at the same time point as the trough inhibitor and ADA samples taken predose.

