- cc* Patient-Reported Outcomes Measurement Information System (PROMIS) Assessments to include Pain Intensity, Pain Interference (PROMIS Pediatric-SF Pain Interference <18 years old), and Physical Function (PROMIS Pediatric-SF Physical Activity <18 years old). The PROMIS instruments will be administered to participants \geq 8 years old and to parent proxy for participants aged 5-12 years.
- dd* The Haemo-QoL children version will be administered to participants \geq 4 years old and the parent will be administered a parent proxy version (\geq 4 years old).
- ee* The EQ-5D-Y children version will be administered to participants \geq 8 years old and the parent version will be administered to parent proxy (for participants 4-7 years old).

Table 2 - PK sampling schedule of activities (PK subgroup)

Assessments ^a	Pre-dose	Post-dose ^c				
	Day 1 Week 1 ^b	Day 1 Week 1		Day 2	Day 4	Day 8 ^d
		15 minutes (±3) minutes	3 hours (±15 minutes)	24 hours (±2 hours)	72 hours (±5 hours)	168 hours (±5 hours)
FVIII activity (measured by one-stage clotting aPTT and two-stage chromogenic assays) ^e	X	X	X	X	X	X

Abbreviations: aPTT = activated partial thromboplastin assay; FVIII = Factor VIII; PK = pharmacokinetics.

NOTE: Initial dosing of BIVV001 is in the clinic on Day 1 Week 1.

- a For a subset of participants who are in the PK subgroup (n=24). Baseline PK sampling can be conducted optionally after full enrollment of the PK subgroup in other participants at the discretion of investigator through central laboratory.
- b Washout of at least 96 hours (4 days) for 6 to <12 years participants and at least 72 hours (3 days) for <6 years participants prior to sample collection is required. Pre-dose samples are collected within 30 minutes prior to dosing. The washout period may be modified at the discretion of the Investigator based on individual PK data and clinical phenotype in consultation with medical monitor.
- c All sampling times are relative to the start of injection.
- d Before injection of the next dose of BIVV001. Study drug can be taken after assessments on Day 8.
- e Details regarding sample handling and volume in relation to body weight are provided in the Central Laboratory Manual.

Table 3 - Surgical schedule of activities

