6.1.2 Study treatment schedule and administration

Instructions for the preparation and administration of BIVV001 are provided in the Pharmacy Manual and the Information for Patients.

The prophylactic treatment regimen is QW (every 7 days) dosing with 50 IU/kg BIVV001. This dose was determined based on population PK model and appropriate simulations to understand steady state kinetics of BIVV001. The aim of the 50 IU/kg QW treatment regimen is to provide sustained FVIII activity levels in the normal to mild hemophilic range and to decrease treatment burden with QW dosing.

The dosing interval in the younger age cohort (<6 years) may be reduced by 1 or 2 days if clinically warranted at the discretion of the investigator and only after consultation with the study medical monitor. For participants who have their BIVV001 dosing interval reduced, the washout period prior to inhibitor tests must be adjusted accordingly.

BIVV001 will be delivered via a slow push IV injection at a rate of administration listed in [Table 6](#) and determined by the participant's comfort level. BIVV001 formulation contains sucrose and the injection durations listed in [Table 6](#) are consistent with recommendations on infusion rates. Overall, the recommended maximum total injection time should be ≤ 15 minutes for all doses.

Table 6 - BIVV001 weight-based vial and injection rate recommendations

Participant weight	Minimum injection duration per vial	Maximum total injection time
10-<20 kg	6 minutes per vial	15 min
20-<30 kg	3 minutes per vial	15 min
≥ 30 kg	2 minutes per vial	15 min

Any missed of BIVV001 doses should be taken as soon as possible or according to the instructions of the Investigator, taking into account that 2 consecutive prophylactic doses of 50 IU/kg should be separated by a period of at least 72 hours.

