8.5 PHARMACOKINETICS

Pharmacokinetic sampling will be conducted as outlined in the sections that follow. Detailed guidelines of washout and PK sampling requirements for baseline and bleeding scenarios are provided in Appendix 7, [Section 10.7.4](#). If a participant has a bleed during the PK time period ([Table 2](#)), the participant's caregiver should enter the bleed into the ePD, contact the Investigator as soon as possible and follow the criteria given in Appendix 7, [Section 10.7.4](#).

The first 24 participants from the 2 age cohorts (12 participants <6 years of age and 12 participants 6 to <12 years of age) will undergo an evaluation of the PK profile of BIVV001 and will be included in the PK subgroup. After completing the baseline PK assessments, these 24 participants will begin QW 50 IU/kg prophylactic treatment with BIVV001. Any participant who does not have adequate PK data will be excluded from the PK analysis. Additional participants may be enrolled to ensure that at least 24 participants have adequate PK data for analysis. The remaining participants will proceed directly to QW prophylactic treatment. Baseline PK sampling can be conducted in other participants at the discretion of investigator through the central laboratory.

During study visits, for reliable PK assessment, PK sampling should not be done via the same intravenous access route as used for the BIVV001 administration.

PK Subgroup: At least 12 participants <6 years of age and at least 12 participants 6 to <12 years of age will undergo PK sampling (up to 168 hours) for BIVV001 activity as follows:

- Dosing at Day 1: single dose of BIVV001 50 IU/kg administered under medical supervision (using a partial vial and actual potency dosing, see [Section 6.1.6.1](#))
- Baseline PK sampling at BIVV001 Day 1: Pre-injection and 15 (± 3) minutes, 3 hours (± 15 minutes), 24 (± 2) hours [Day 2], 72 (± 5) hours [Day 4], and 168 (± 5) hours [Day 8] from the start of the injection

See [Table 2](#) for details of PK sampling of first 12 participants in each age cohort. If a participant has a bleed during the PK time period above, the participant's caregiver should enter the bleed into the ePD and contact the Investigator as soon as possible.

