
Day 1 Baseline PK sampling: 12 subjects 6 to <12 years of age
	
Washout
 
 • First attempt: Washout of at least 96 hours (4 days); repeat this washout if participant treats a bleed prior to 96 hours (follow second attempt)^a. • Additional attempt(s): Conduct same washout as first attempt. If the second attempt at washout fails, additional attempts may be considered after consultation with the medical monitor^a. 
PK Sampling
 
 • First attempt: PK sampling period with collection of PK samples (Table 2) to 168 hours (Day 8) is required. If a participant treats a bleeding episode after receiving the dose of BIVV001 for PK evaluation but prior to completing the PK sampling period, PK sampling will be stopped at the time of the bleed and a second attempt PK sampling period should be conducted.

- Second attempt: Participants are required to undergo a 240 hour washout^a after previous dose, which is then followed by the PK sampling period with collection of PK samples (Table 2) to 168 hours (Day 8).
- If the second attempt at PK sampling period fails due to the participant treating a bleed prior to collection of the 168-hour (Day 8) sample, the participant will remain in the study but will no longer be included in the PK subgroup. The participant will be replaced in the PK subgroup and will continue with prophylactic BIVV001 dosing regimen.

Peak and trough sampling: All Participants except PK subgroup at Day 1

Washout

- First attempt: Washout of at least 72 hours (3 days) or 96 hours (4 days) for < 6 yr and 6 to <12 yr participants, respectively; repeat this washout if participant treats a bleed prior to 72 hours and 96 hours for <6 yr and 6 to <12 yr participants respectively (follow second attempt)^a.
- Additional attempts: Conduct same washout as first attempt.
- If the second attempt at washout fails, additional attempt may be considered after consultation with the medical monitor.

PK Sampling

- Collection of sample at trough (immediately pre-injection) and peak at 15 ±3 mins from start of injection. If the participant is being treated for an acute bleeding prior to collection of the peak and trough sample collection, no repeat sampling is needed and the patient will remain in the study and collect peak and trough at the next scheduled visit.

Peak and trough sampling: All Participants after Day 1

Washout

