- No washout required. Participants should visit clinic 7 ±1 day after previous dose.
- If the participant has treated a bleeding episode since his last dose, the scheduled visit should be postponed for 7 ±1 day after previous dose.

PK Sampling

[figure not shown]
- Collection of sample at trough (immediately pre-injection) and peak at 15 ±3 mins from start of injection. If the participant treats a bleed prior to collection of the peak and trough sample collection, no repeat sampling is needed and the participant will remain in the study and collect peak and trough at the next scheduled visit.

^a The washout period may be modified at the discretion of the Investigator based on individual PK data and clinical phenotype in consultation with medical monitor

[figure not shown]

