- For each assay type, a summary table of FVIII activity levels will be provided for BIVV001 at scheduled PK visits and time points for the PK subgroup (Baseline BIVV001). Summary descriptive statistics will include the number of non-missing values, mean, geometric mean, standard deviation, percent coefficient of variation, minimum, and maximum. In these summaries, values below the LLOQ will be imputed as zero.
- For each assay type, individual PK parameters will be listed for each participant and summarized descriptively for the PK subgroup (Baseline BIVV001). Any FVIII assessments flagged by the PK scientist as being implausible and excluded from computation of PK parameters will be excluded from summaries but included in listings. The listings will indicate which values, if any, were excluded from summaries. A separate listing of excluded values, together with the reason for exclusion will be provided.

In addition, for each assay type, the peak and trough concentrations will be summarized by visit for the FAS. The incremental recovery will also be summarized by visit for the FAS. Summary descriptive statistics will include the number of non-missing values, mean, geometric mean, median, Q1, Q3, standard deviation, percent coefficient of variation, minimum, and maximum. In these summaries, values below the LLOQ will be imputed as zero.

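### The same peak FVIII sample is timed from the start of injection in some sections and post-injection in others, so an on-time peak can be drawn before a long injection has ended

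*Protocol*

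**What the plan says.** **Counted from the start of injection.**
- Protocol section 1.3, Table 2 footnote c (PK subgroup): "All sampling times are relative to the start of injection".
- Section 8.5 lists the Baseline PK samples, from the 15 (±3) minute one onward, ending with "168 (± 5) hours [Day 8] from the start of the injection".
- Section 10.7.4 repeats the rule for participants outside the PK subgroup at Day 1 ("peak at 15 ±3 mins from start of injection") and for all participants after Day 1 ("Collection of sample at trough (immediately pre-injection) and peak at 15 ±3 mins from start of injection").

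**Counted post-injection.**
- Table 1 footnote bb sets the scheduled-visit peak at 15 (±3) "minutes post-injection, respectively. This trough sample should be collected at the same time point" as the pre-dose inhibitor and antibody samples.
- Section 4.1 says post-injection twice, once for Baseline and once for the scheduled visits.

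**How long an injection may take.** Section 6.1.2 states that "the recommended maximum total injection time should be ≤ 15 minutes for all doses". Table 6 adds a minimum per vial: 6 minutes at 10 to <20 kg, 3 minutes at 20 to <30 kg and 2 minutes at 30 kg or more.

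**How the data are used.** Table 1 footnote k has injection start and stop times recorded in the eCRF. SAP section 4.8.1 uses actual sampling times and injection durations for the PK analysis, but nominal sampling times for tables, figures and listings. It also summarizes peak and trough by visit for the FAS and adds: "The incremental recovery will also be summarized by visit for the FAS".

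**The concern.** Footnote bb and the second 10.7.4 entry govern the same sample, the scheduled-visit peak after Day 1. The difference is therefore not one between the PK subgroup and the other participants. If post-injection means after the end, a site following one passage draws off schedule under the other.

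The start-based rule carries a further risk, because its window opens before the longest permitted injection closes. Sections 6.2.4 and 8.5 ask for PK samples through a different venous access from the one used for dosing, so a draw during the injection is physically possible. No passage requires the injection to be finished first, and no analysis rule removes a peak drawn too early.

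Cmax and incremental recovery are secondary PK endpoints summarized by age cohort. A peak drawn mid-injection understates both.

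**Working it through.** The plan states no figure to reproduce, so this is direct arithmetic on its timing rules.

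**1. The two windows.** For an injection lasting T minutes, measured from its start:
- start-based: 15 ± 3 = 12 to 18 minutes;
- end-based: T + 12 to T + 18 minutes.

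At T = 6 these touch only at 18 minutes, and for any longer injection they do not overlap. At T = 15 they are 12–18 and 27–33 minutes.

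**2. When the start-based draw is mid-injection.** The draw time must be below T. The earliest draw is at 12 minutes and T may not exceed 15, so this requires 12 < T ≤ 15.

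**3. How long injections need to take.** At 50 IU/kg, a child of 10 to <20 kg needs 500 to <1000 IU. Vials are 250, 500, 1000 and 2000 IU.
- One vial (500 IU at 10 kg, 1000 IU above that) has a minimum of 6 minutes.
- Two vials (500 + 250 IU, for more than 10 and up to 15 kg) have a minimum of 2 × 6 = 12 minutes, exactly when the window opens.
- Three vials would need 18 minutes, above the 15-minute maximum.

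For a two-vial dose at the Table 6 minimum, the start-based window falls this long after the end of injection:

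| Weight | Minimum duration | Time from end of injection to draw |
|---|---|---|
| 10 to <20 kg | 12 min | 0 to 6 min |
| 20 to <30 kg | 6 min | 6 to 12 min |
| 30 kg or more | 4 min | 8 to 14 min |

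**4. Size of the loss.** The model is one compartment, a constant rate and immediate mixing, with k = ln 2 / half-life. Activity relative to an instantaneous bolus is
- (1 − e^(−kt)) / (kT) for t ≤ T;
- (1 − e^(−kT)) / (kT) × e^(−k(t−T)) afterwards.

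The half-life of 37–44 h is the adult range in Protocol section 2.2.3.2. A lower value of 25 h is my assumption, to allow for faster clearance in children. With T = 15 minutes:

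| Draw, from start | 25 h (assumed) | 37 h | 44 h |
|---|---|---|---|
| 12 min | 0.798 | 0.799 | 0.799 |
| 13 min | 0.864 | 0.865 | 0.865 |
| 14 min | 0.930 | 0.931 | 0.932 |
| 18 min | 0.995 | 0.997 | 0.997 |
| 30 min (15 after end) | 0.990 | 0.993 | 0.994 |
| 3 h | 0.923 | 0.948 | 0.956 |

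The first row is essentially 12/15 = 0.80, whatever the half-life. Taking recovery as the rise in activity per unit dose (the documents give no formula), it falls in the same proportion.

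**5. What the 3-hour sample protects.** Observed Cmax is the larger of the first and 3-hour values. In the PK subgroup's Baseline profile, the shortfall against the bolus value is therefore at most 1 − 0.956 = 4.4% to 1 − 0.923 = 7.7%. Peak-and-trough visits have no second post-dose sample.

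**6. Cost of waiting.** Decay over 15 minutes is 1 − 2^(−0.25/37) = 0.5% at 37 h and 0.4% at 44 h.

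**The case against.** **The wording may be shorthand.** Table 2 heads its samples as post-dose and then defines them from the start, and footnote bb could be read likewise, since it never mentions the end of injection. That is a fair reading. It removes the contradiction but leaves every peak start-based, so the mid-injection possibility then applies at all visits.

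**Long injections are not the default.** One vial can cover any dose at 10 to <20 kg, with a 6-minute minimum, and the draw then falls 6 to 12 minutes after the end. Vial selection is left to the Pharmacy Manual, which is not among the documents. The 20% figure needs the longest permitted injection and the earliest permitted draw. All of this stands. Once the injection has finished, the choice of reference changes the modelled value by less than 1%.

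**Safeguards exist.** Stop times are recorded, actual durations enter the PK analysis, and the PK scientist may exclude implausible values. These identify an affected sample but cannot restore the missed peak. A value up to 20% low need not look implausible, and the by-visit FAS summaries have no timing rule.

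**A reader might infer that the start-based rule biases the under-6 cohort downward** and makes the age contrast a timing artefact. The documents do not support that. They give no weights by age, the 15-minute maximum applies to every band, and Protocol section 9.1 plans no formal comparison. Nor can Cmax be called 20% low in general, given the 3-hour sample.

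**Conclusion.** The inconsistency in the time reference is real and should be reconciled. Under the start-based reading, a peak drawn on time at 12 to just under 15 minutes can precede the end of a permitted injection. The loss in peak and incremental recovery is then up to about 20%, falling to about 7% for a draw at 14 minutes of a 15-minute injection. It arises only when an injection exceeds 12 minutes, and the documents do not show how often that will happen.

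The exposure is mainly in the by-visit FAS summaries of peak and recovery; Baseline Cmax in the PK subgroup is limited to about 4–8%. Because minimum times are longest in the lightest children, the cohorts could be affected unequally, but that is a possibility rather than a demonstrated bias.

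The sizes assume a constant injection rate, one compartment and immediate mixing. The 4–8% also depends on the half-life range, of which only 37–44 h comes from the documents.

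**What to change.** **Protocol.** Bring Table 1 footnote bb, Table 2 footnote c and sections 4.1, 8.5 and 10.7.4 to one stated reference for the peak, and say that it is drawn only after the injection is complete. One way is 15 ± 3 minutes after the end of injection, with actual times still recorded from the start and the other Table 2 times unchanged. Footnote c would then need to name the peak as its exception.

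**SAP section 4.8.1.** Exclude from the Cmax, peak and incremental recovery summaries, and list, any peak sample whose recorded time precedes the recorded injection stop. State whether Cmax for such a Baseline profile is then taken from the 3-hour sample or set to missing. Apply the rule to samples already drawn: the first participant was enrolled on 22-Mar-2021, before the SAP date of 23-Aug-2021.

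**Cost.** One protocol clarification and a short SAP addition. No extra sample or visit is needed, and injection times do not change. A few peak values may be lost. Samples already drawn may follow either reference, so the listing should show which was used.

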2 INTRODUCTION

Recombinant coagulation Factor VIII Fc - von Willebrand factor - XTEN fusion protein (rFVIII_{FC}-VWF-XTEN) (BIVV001; BIIB073) is designed to be a new class of blood clotting FVIII product. As with existing FVIII products, BIVV001 temporarily replaces the missing FVIII needed for effective hemostasis in hemophilia A patients.

BIVV001 is a novel fusion protein consisting of single-chain B-domain deleted (BDD) human FVIII, the Fc domain of human immunoglobulin G1 (IgG1), FVIII-binding D'D3 domain of human von Willebrand factor (VWF), and 2 XTEN polypeptide linkers (Figure 2) (1). The Fc, VWF, and XTEN linker portions of the molecule are each designed to extend the $t_{1/2}$ of the FVIII molecule in plasma.

Figure 2 - Overall design and components of BIVV001

2.1 STUDY RATIONALE

BIVV001 is designed to be a new class of blood clotting FVIII. Preclinical and clinical experience indicate that BIVV001 has an extended half-life, which can achieve and maintain higher sustained factor activity levels than currently available treatments, with less frequent administration.

This study is being conducted to determine the safety, efficacy, and PK of BIVV001 administered as QW prophylaxis treatment in PTPs <12 years of age with severe hemophilia A.

2.2 BACKGROUND

Hemophilia A is a congenital X-linked bleeding disorder that occurs predominantly in males and is characterized by deficiency of functional FVIII. It is caused by any of a variety of mutations of the coagulation FVIII gene, including missense or nonsense mutations, gene deletions, inversions, and splice junction mutations (2, 3). The worldwide prevalence of hemophilia A is estimated to be 1 in 10,000 and worldwide incidence is approximately 1 in 5000 male births (4). Hemophilia A appears to be equally distributed across the world (5, 6, 7). The severity of disease is characterized by the endogenous level of FVIII measured in the plasma. Severe hemophilia A (<1% endogenous FVIII activity level [ie, <1 IU/dL]) accounts for approximately 30% to 50% of all cases of hemophilia A (8, 9, 10).

Individuals with severe hemophilia experience frequent bleeding episodes into major joints, soft tissue, and muscle, either spontaneously or following minor trauma. The disease can be acutely life-threatening. Repeated bleeding can lead to debilitating long-term complications, including hemophilic arthropathy from bleeding into the joints (7). Another severe complication is the development of target joints from inflammation due to prior bleeding. Intracranial hemorrhage can result in disability and death and is the leading cause of hemorrhagic death in individuals with hemophilia (11). Significant effects on physical and psychosocial well-being and quality of life (QoL) and substantial financial burden have been reported in patients with severe hemophilia (12).

